Thirty persons with MS will be randomized to either placebo or smoked cannabis. Patients will be assessed before and after treatment for 3 consecutive days (phase I); undergo wash out for a total of 11 days; and then cross over to either placebo or active treatment (phase II) depending on what they received during Phase I. Since each phase of treatment requires 2 assessments (before and after inhaled product) on each of 3 consecutive days, the study will allow comparisons to be made on spasticity, cognitive, neuropsychiatric, safety and global measures before and after treatment with cannabis or placebo for a total of twelve assessments. Blood will be drawn for quantitative analysis of serum THC before and immediately following each treatment session as an estimate of systemic exposure.

Considering start-up time, training and recruitment of personnel, procurement of equipment and supplies, and unanticipated initial delays, we expect that one-third (n=10) of the required subjects will be recruited and tested during the first year and that the remaining two-thirds (n=20) of the required subjects will be recruited and tested during the second year of the study.

The following schedule of visits is planned:

	Screening I	Screening II	PHASE I Treatment Days 1-3		Washout (Days 4-14)	PHASE II Treatment Days 15-17	
			B	A		B	A
Consent	x						
Eligibility Checklist	x	x					
Medical Hx/Screens	x						
Concomitant meds	x	x					
Urine Toxicology	x		x#			x#	x#
Adverse Events			x	x		x	x
EDSS		x					
Modified Ashworth Scale	x	x	x	x		x	x
Timed 25-ft Walk		x	x	x		x	x
Pain Analog Scale			x	x		x	x
Cognitive Battery		x	x	x		x	x
Neuropsychiatric Assessment		x	x	x		x	x
Tx Emergent Effects				x			x
MSQLI			x†	x†		x†	x†
Practice Session		x					
THC Assays			x	x		x	x

B=before treatment; A=after treatment; †=Days 1, 3 and 15, 17 only; #= Days 1,15, and 17 only

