Patients will then return to the CRC to begin **Phase I** treatment within 7 days of Screening Visit II. At baseline (**Day #1**), urine will be collected for toxicologic screen. A positive toxicologic screen for drugs of abuse including cannabis will exclude the patient from further participation. The Modified Ashworth Spasticity Scale, Timed 25-ft Walk, Visual Analog Scale of Pain, cognitive battery, neuropsychiatric assessments, and MSQL-I will be administered. Blood will be drawn for total THC. Following their first treatment session with smoked product, blood will be drawn for peak THC levels and patients will be assessed on the Modified Ashworth Spasticity Scale, Timed 25-ft Walk, Visual Analog Scale of Pain, cognitive battery, neuropsychiatric assessments, and treatment-emergent effects beginning 30 minutes after their treatment session. On **Day #2**, they will return to the CRC at approximately the same time of day to ensure regulation of food, medication, and time of cannabis intake. Blood will be drawn for total THC. Patients will be assessed with the Modified Ashworth Spasticity Scale, Timed 25-ft Walk, Visual Analog Scale of Pain, cognitive battery, and neuropsychiatric assessments. Following treatment with smoked product, blood will be drawn for peak THC levels and patients will again be assessed on the Modified Ashworth Spasticity Scale, Timed 25-ft Walk, Visual Analog Scale of Pain, cognitive battery, neuropsychiatric assessments, and treatment-emergent effects, beginning 30 minutes after their treatment session. On **Day #3**, the patient will return to the CRC at approximately the same time of day for their third treatment. Blood will be drawn for total THC. Patients will undergo assessment with the Modified Ashworth Spasticity Scale, Timed 25-ft Walk, Visual Analog Scale of Pain, cognitive battery, and neuropsychiatric assessments. Following completion of the third treatment, blood will be drawn for peak THC levels and patients will be assessed with the Modified Ashworth Spasticity Scale, Timed 25-ft Walk, Visual Analog Scale of Pain, cognitive battery, neuropsychiatric assessments, treatment-emergent effects, and MSQL-I.

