Patients will take no treatment for the next eleven days and will return to the CRC to begin Phase II on **Day #15**. A positive toxicologic screen for drugs of abuse other than cannabis will exclude the patient from further participation. (A positive urine toxicologic screen for cannabis and a peak plasma THC concentration greater than Day #3 will suggest illicit use and exclude the patient from further participation.) The Modified Ashworth Spasticity Scale, Spasm Frequency Score, Timed 25-ft Walk, Visual Analog Scale of Pain, cognitive battery, neuropsychiatric assessments, and MSQL-I will be administered. Blood will be drawn for total THC. Patients will undergo treatment with smoked product and blood will be drawn for peak THC levels. Patients will be assessed on the Modified Ashworth Spasticity Scale, Timed 25-ft Walk, Visual Analog Scale of Pain, cognitive battery, neuropsychiatric assessments, and treatment-emergent effects, beginning 30 minutes after their treatment session. Patients will return to the CRC at approximately the same time of day on **Day #16**. Blood will be drawn for total THC. Patients will be assessed on the Modified Ashworth Spasticity Scale, Timed 25-ft Walk, Visual Analog Scale of Pain, cognitive battery, and neuropsychiatric assessments. Following treatment with smoked product, blood will be drawn for peak THC levels and patients will again be assessed on the Modified Ashworth

Appendix to: [name], [name], [name], et al. Smoked cannabis for spasticity in multiple sclerosis: a randomized, placebo-controlled trial. *CMAJ* 2012. DOI:10.1503/cmaj110837.

Copyright © 2012 Canadian Medical Association or its licensors

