Treatment Emergent Effects of cannabis will be assessed after each treatment by interview and self-report of physical and psychological symptoms using the Subjective Ratings of High and Sedation - Revised (SRHS-R) and the UKU Side Effect Rating Scale. The **Subjective Ratings of High and Sedation - Revised** has been adapted from Block, et al (1998) for use in the present study to evaluate the subjective effects of cannabis. This scale consists of 10 ratings of different aspects of stimulation vs. sedation (alert/drowsy, attentive/dreamy, tense/relaxed, interested/bored, capable/incompetent, excited/calm, clear-headed/fuzzy, well-coordinated/clumsy, quick-witted/mentally slow, and energetic/lazy). The **UKU Side Effect Rating Scale** is a semi-structured interview that evaluates a wide range of unwanted side effects including psychological (eg, concentration difficulties, failing memory, lassitude), neurological (eg, hypokinesia, paraesthesias), autonomic (eg, accommodation disturbance, orthostatic dizziness, nausea, sweating), and miscellaneous effects (eg, weight gain, diminished sexual desire) (Lingjaerde et al 1986). Each treatment emergent symptom is defined on a four-point scale of intensity (0 = not present; 3 = severe), and rated separately with regard to being causally related to the study drug (improbably related, possibly related, probably related). In addition, sitting and standing blood pressure, heart rate, respirations, and oral temperature will be obtained before

Appendix to: [name], [name], [name], et al. Smoked cannabis for spasticity in multiple sclerosis: a randomized, placebo-controlled trial. *CMAJ* 2012. DOI:10.1503/cmaj110837.

Copyright © 2012 Canadian Medical Association or its licensors

drug administration and at 0.5, 1 and 2 hours after administration to monitor the subject's health status as well as to quantify cannabis's general effects.

Quality of Life (administered at the beginning and end of each phase):

The **Multiple Sclerosis Quality of Life-Inventory** is both a generic and an MS-specific quality of life measure (Coulthard-Morris, 2000). It consists of 138 items and 10 separate scales that assess the following domains: general health status, fatigue, pain, sexual satisfaction, bladder control, bowel control, vision, cognitive function, mental health, and social support. It is self-administered and takes about 30 minutes to complete.

7. Laboratory Assessments

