Hypothesis #2: Smoking medicinal cannabis will result in impairment on cognitive measures of attention, concentration, and memory in addition to adverse neuropsychiatric features as measured by the Paced Auditory Serial Addition Test, Brief Symptom Inventory, Perceived Deficits Questionnaire, Modified Fatigue Impact Scale, the Subjective Ratings of High and Sedation - Revised, and UKU Side Effect Rating Scale. Means and bootstrap-based bias-corrected confidence intervals will be computed for each assessment time of each specified measure. For each subject the response is the change between a before-after placebo difference and a before-after treatment difference on the specified measures where before and after treatment measurements were taken (e.g. PASAT), and a change between the post-placebo and post-active scores when only the post-treatment measurements were taken (e.g. SRHS-R). We will evaluate the aggregate differences using a one-sample t-test (i.e. perform a paired-sample t-test). Here again we define as clinically important any departure from zero in the hypothesized direction that is greater than one standard deviation of paired differences. In

Appendix to: [name], [name], [name], et al. Smoked cannabis for spasticity in multiple sclerosis: a randomized, placebo-controlled trial. *CMAJ* 2012. DOI:10.1503/cmaj110837.

Copyright © 2012 Canadian Medical Association or its licensors

addition the relationship between total plasma THC and cognitive, neuropsychiatric and treatment-emergent effect scores will be examined using Pearson correlation.

Hypothesis #3: Smoking medicinal cannabis will result in improvement in global abilities and quality of life as measured by the Multiple Sclerosis Quality of Life-Inventory. For each subject the response is the change between a post-placebo and a post-treatment score on the MSQOL-I. The aggregate differences will be evaluated using a one-sample t-test (i.e. perform a paired-sample t-test).

Regression and covariate analysis will also be applied to determine the association between the major efficacy/safety outcomes and important clinical variables such as EDSS score, smoking history, exhaled CO levels, concomitant medications, etc.

E. HUMAN SUBJECTS

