A total of 30 individuals will be enrolled over a two-year period. Individuals will be recruited as participants based upon specific medical and treatment characteristics, detailed previously as inclusion and exclusion criteria. All participants will be fully informed by trained personnel regarding the potential risks and benefits of participating in medical research. The purpose of the research, the schedule of visits, and the procedures to be performed will be fully explained. Participants will be informed that they may discontinue participation at any time and that discontinuation will not affect their future medical care. This information is also provided in a written document. After reviewing this document and asking any questions, the participant is asked to sign, indicating an awareness of the study requirements and a desire to take part in the research study. This consent is witnessed and is signed by medically competent personnel. The participant receives a copy of his/her signed consent forms (containing a name and contact number in case of emergency) and the original form is retained. The participant also receives a copy of "The Experimental Subject's Bill of Rights".

Potential Risks. Potential risks of data collection in this study include mental and/or emotional distress that may result from questions asked during assessment or as a result of the time taken in the assessment process. In addition, some neuropsychological tests may require concentrated effort and may be frustrating to the participant to complete. There are no potential physical risks posed by neurobehavioral examinations. Standard risk is associated with venipuncture include pain, bruising, and a very low risk of infection. Risks of inhaled cannabis products may include psychomotor coordination difficulties, eye irritation, throat irritation, increased heart rate, possible hypotension, reversible appetite/mood/memory/cognition effects. Smoking marijuana may prejudice application for future employment, if drug screening is a condition of employment. It is likely that detectable traces of marijuana will remain in the hair or blood for a minimum of six weeks after smoking.

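### Hypothesis #3 tests quality of life on post-phase scores alone and gives up precision by leaving unused the pre-dose scores collected in each phase

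*Protocol*

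**What the plan says.** Section D.8 (Statistical Considerations), Hypothesis #3, fixes the response: "For each subject the response is the change between a post-placebo and a post-treatment score on the MSQOL-I". It then fixes the test: "The aggregate differences will be evaluated using a one-sample t-test (i.e. perform a paired-sample t-test". Neither sentence mentions a baseline, period or sequence term.

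The data collected go further than that. Section D.6 introduces the instrument with "Quality of Life (administered at the beginning and end of each phase", and the footnote to the visit table in D.1 limits it to "Days 1, 3 and 15, 17 only". The narrative in D.1 puts a pre-dose administration at the start of each phase:

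- Day 1: "cognitive battery, neuropsychiatric assessments, and MSQL-I will be administered. Blood will be drawn for total THC. Following their first treatment session with smoked product".
- Day 15: "cognitive battery, neuropsychiatric assessments, and MSQL-I will be administered. Blood will be drawn for total THC. Patients will undergo treatment with smoked product".

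The post-dose administrations are on Days 3 and 17. I take MSQLI, MSQL-I and MSQOL-I as names for one instrument.

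Elsewhere in D.8, Hypothesis #1 contrasts the before-after difference on cannabis with that on placebo. Hypothesis #2 does the same for measures with both scores, and keeps the post-only contrast for measures taken only after treatment.

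**The concern.** The questionnaire has a pre-dose and a post-dose score in each phase, yet it is analysed as if only the second existed. Two of the four administrations of a 138-item instrument play no part in the only test of Aim #3. Hypothesis #3 also departs, without a stated reason, from how the same section treats other measures with both scores.

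At stake is precision in a trial of 30 patients: a wider interval for quality of life than the collected data allow. A shift between phases that is left out of the model adds to this. The primary outcome, the Modified Ashworth Scale, is not touched, because Hypothesis #1 already uses both scores.

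**Working it through.** **The protocol's own figure.** The only power statement stands under Hypothesis #1: 30 patients, α = 0.05, effect of one SD of the paired differences, power well over 80%. With the noncentral t (29 degrees of freedom, noncentrality √30 × 1), two-sided power is 99.96%. The figure reproduces and is not in dispute. No power is stated for Hypothesis #3. With 30 patients, 80% two-sided power corresponds to an effect of 0.53 SD.

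**Inputs not in the protocol.** It gives no SD, correlation, period shift or carry-over for the MSQLI, so the values below are assumptions.

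**1. Precision.** Let r be the correlation across patients between the baseline difference (cannabis phase minus placebo phase, pre-dose) and the post-phase difference, with equal variances at both times. Relative to the post-only variance, covariate adjustment gives 1 − r² and the simple change score gives 2(1 − r).

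| r | Covariate | Saving | Change score | Post-only patients needed to match 30 adjusted |
|---|---|---|---|---|
| 0.3 | 0.91 | 9% | 1.40 | 30/0.91 ≈ 33 |
| 0.5 | 0.75 | 25% | 1.00 | 30/0.75 = 40 |
| 0.7 | 0.51 | 49% | 0.60 | 30/0.51 ≈ 59 |

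If rw is the correlation of scores within a phase and rb that between phases, r = (rw − rb)/(1 − rb). At rb = 0.7, rw = 0.8 gives r = 0.33 and a factor of 0.89; rw = 0.9 gives r = 0.67 and 0.56. The change score has 1.33 and 0.67 times the post-only variance in these two cases. It beats the post-only contrast only if r exceeds 0.5.

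These factors ignore the cost of estimating the slope. In a simulation with 30 patients, that cost raised the variance by about 4% when r was 0.

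**2. Period shift.** Let Phase II scores differ from Phase I by p, in SDs of the paired differences. The cannabis-minus-placebo difference moves by −p in patients who get cannabis first and by +p in the others. With a share f getting cannabis first, the bias of the post-only mean is −p(2f − 1).

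- 15:15 (f = 0.5): bias 0. The SD grows by √(1 + p²), which is √1.25 = 1.12 at p = 0.5. At an effect of 0.53 SD, simulated power falls from about 80% to 73%, and the type I error is 2.7%, so the test is conservative.
- 18:12 (f = 0.6), p = 0.5: bias −0.5 × 0.2 = −0.10.
- 20:10 (f = 0.67), p = 0.5: bias −0.5 × 0.33 = −0.17.

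The protocol does not state how the sequences are balanced. Under simple 1:1 randomization of 30, a split of 18:12 or worse has probability of about 36%.

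**3. Carry-over.** Let cannabis given in Phase I leave an effect Lb at the Day 15 baseline and Lp at Day 17, with 15:15 sequences. The bias is −Lp/2 for post-only, (Lb − Lp)/2 for the change score, and (r × Lb − Lp)/2 for the covariate model with a period term, where the slope equals r. With Lb = 0.4 and r = 0.5:

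| Lp | Post-only | Covariate | Change score |
|---|---|---|---|
| 0.4 | −0.20 | −0.10 | 0 |
| 0.2 | −0.10 | 0 | +0.10 |
| 0 | 0 | +0.10 | +0.20 |

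No choice is free of carry-over bias in every row.

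**The case against.** The strongest reply is that a post-only paired contrast is a sound crossover estimator without carry-over, and can be more precise than a change score. That stands, and it is why the remedy is a covariate and not subtraction. It is also fair that the Hypothesis #2 wording describes that hypothesis's own measures, so Hypothesis #3 departs from a pattern and breaks no general rule. The gain rests on an assumed r: if pre-dose and post-dose scores in one phase agree no better than scores from different phases, r is 0 and nothing is gained.

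Leaving the matter to an analysis plan is a weaker reply. The protocol is not silent here: it defines both response and test. The closing regression sentence in D.8 concerns associations with clinical variables such as disability and smoking history. It does not name the phase baseline or change this test.

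Three stronger readings are tempting, and the document does not support them.

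- A reader might infer that disease drift over the 14 days between Day 3 and Day 17 goes straight into the estimate. With equal sequences it cancels from the mean.
- A reader might set "Patients will take no treatment for the next eleven days" against "It is likely that detectable traces of marijuana will remain in the hair or blood for a minimum of six weeks after smoking" and see a contradiction. The second statement, in Section E, concerns detection and follows a remark on drug screening by employers. The same paragraph calls effects on mood and cognition reversible. D.1 also foresees a positive cannabis screen on Day 15 and has a rule for it. Traces are not evidence of a lasting effect on quality of life.
- A reader might note the 10 scales and compute 1 − 0.95^10 = 40% for a false positive. The protocol nowhere plans ten tests. Scoring and multiplicity for an outcome that is not primary are commonly left to the analysis plan, and the figure assumes independent scales.

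**Conclusion.** The point holds as a loss of precision that costs almost nothing to avoid. It does not make the Hypothesis #3 test invalid. The response leaves out two scheduled pre-dose scores and differs without explanation from Hypotheses #1 and #2. The variance that could be saved is 9%, 25% or 49% at r of 0.3, 0.5 or 0.7, before the small cost of estimating the slope; r is an assumption throughout. A period shift left out of the model widens the interval further, and it biases the estimate only when the sequences are unequal.

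The documents do not show that carry-over exists, and using the baselines would not in general remove it. The point concerns Aim #3 only.

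**What to change.** Redefine the Hypothesis #3 analysis. Regress the within-subject post-phase MSQLI difference (cannabis minus placebo) on the pre-dose baseline difference and a sequence-order term that carries the period effect. Read the treatment effect at a baseline difference of zero, averaged equally over the two sequences. A linear model with a fixed subject effect, treatment, period and the phase's own baseline gives the same estimate. Do not use simple change scores, which can be less precise. If the sponsor prefers the post-only contrast, the protocol should say why.

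Report Day 15 minus Day 1 pre-dose MSQLI by sequence, labelled as a descriptive, low-power look at carry-over and not as a test that decides the analysis.

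The cost is wording only, since every score is already scheduled. Residual degrees of freedom fall from 29 to 27 with 30 completers. The one real drawback is that the adjusted estimate shifts if carry-over is present on Day 15 but gone by Day 17.
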